5.5.1.2. Handling of Dropouts or Missing Data

No imputation method will be used for a visit if a certain measure at the visit is determined as missing. For example, if the compliance rate for each monthly interval is $\leq 50\%$, then all endpoints to be derived from the diary data for that 1-month period will be considered missing; otherwise, the endpoints at that month (visit) is not missing.

Please refer to Section 5.4.1 for approach to handling missing diary data for derivation of the number of migraine headache days and other efficacy measures.

For MMRM analysis on the repeated measures analyses, the model parameters are simultaneously estimated using restricted likelihood estimation incorporating all of the observed data. Estimates have been shown to be unbiased when the missing data are MAR (missing at random).

5.5.1.3. Analysis Populations

Analysis populations are defined below:

All Patients: All patients who signs informed consent.

All Randomized Patients (ARP): All patients who are randomized at Visit 3.

Intent-to-Treat (ITT) Population: All patients who are randomized at Visit 3 and received at least 1 dose of the study drug. Patients in the ITT population will be analyzed according to the treatment to which they were randomized. Unless otherwise specified, the ITT population will be the primary population on which statistical analysis will be performed.

Post-treatment Population: All patients who entered the post-treatment phase (Study Period IV) as indicated by entering any post-treatment visit. Patients in the post-treatment population will be analyzed according to the treatment that they were randomized to at Visit 3. Post-treatment Population is a subset of ARP.

ADA Follow-up Cohort: All patients who are post-treatment population and have both baseline and at least one post baseline ADA assessment during SP IV.

Per Protocol Set (PPS): Intent-to-treat population who has no important protocol deviation, which impacts efficacy analysis. Details will be specified in Section 5.5.3.

Safety Population: This is the same as the ITT population except the assigned arm definition. It is determined by modal treatment the patient received during the treatment period (up to the injection visits if they discontinue early). For determining modal treatment, do not consider the loading dose visit for PLA/LY120 and CM120 patients (newly assigned to LY120-mg treatment group), but do consider it for LY120/LY120, LY240/LY240, PLA/LY240, CM240 patients.

(See arm definitions in Section 5.5.4.) If there are 2 or more modes, then add the loading dose visit and recalculate the mode. If there is still a tie, the highest dose of the modes is to be used.

Example 1: Suppose a CM patient, randomized as LY120-mg treatment group, discontinues at Visit 5 (Month 1) who has LY 240-mg loading dose at Visit 3 (Month 0) and no dose at Visit 5 (Month 1). It implies mode is not unique, because Visit 3 dosing is omitted. Its mode is 0mg, 120mg, 240mg (counted as zero at each dose). Then the patient is assigned to LY240-mg arm group (the highest dose) as safety population.

Example 2: Suppose a patient, randomized as LY120-mg treatment group, discontinues at Visit 6 (Month 2) who has LY 240-mg loading dose at Visit 3 (Month 0), LY 120-mg dose at Visit 5 (Month 1) and no dose at Visit 6. Then the patient is assigned to LY120-mg arm group as safety population.

PPS will be used to create summary table of mean change from baseline in the number of migraine headache days for sensitivity analysis purpose (descriptive summary only).

Unless otherwise specified, safety population is used for safety analysis and exposure.

Unless otherwise specified, statistical analysis for efficacy will be carried out for 12 months treatment phase (Study Period III), 4 months post-treatment phase (Study Period IV) as well as 12 months treatment and 4 months post-treatment phase combined (Study Period III/IV). Detail analysis plan is in [Table CGAP. 5.5](#). Unless otherwise specified, following analysis population will be used:

- For the analyses in Study Period III, the **ITT population** will be used.
- For the analyses in Study Period III/IV, the **ITT population** will be used.
- For the analyses in Study Period IV, the **post-treatment population** will be used.

5.5.1.4. Baseline and Post-Baseline Definition

[Table CGAP. 5.4](#) describes the rules for determining the patient population and baseline and post-baseline observations for each study phase and type of analysis. When “last of Visit x-x” is used in the table, the last nonmissing observation obtained in the visit interval will be used.

Table CGAP. 5.4 Patient Population with Baseline and Post-Baseline Definitions by Study Period and Type of Analysis

Study Period/Analysis	Patient Population	Baseline Observation	Post-baseline Observation(s)
Study Period III			
Efficacy analyses	ITT Population with a baseline and at least 1 post-baseline observation	Visit 3	All Visits 3.01–16
Mean change from baseline in the number of migraine headache days	PPS Population with a baseline and at least 1 post-baseline observation	Visit 3	All Visits 3.01–16
Quality of Life analyses	ITT Population with a baseline and at least 1 post-baseline observation	Visit 3	All Visits 3.01–16
TEAEs	Safety Population	EM: CGAN Visit 1 – CGAP Visit 3 CM: All Visits 1–3. Pre-existing condition that is still ongoing at Visit 1 should be evaluated as baseline values.	All Visits 3.01–16
Serious Adverse Events, Discontinuations due to Adverse Events	Safety Population	NA	All Visits 3.01–16
C-SSRS categorical analyses	Safety population with a baseline and at least 1 post-baseline C-SSRS assessment	EM: Recent History: CGAP Visit 3 All Prior History: All CGAN Visits 1-12 including lifetime ^a CM: Recent History: All CGAP Visits 1–3 excluding lifetime ^a	All Visits 3.01–16

Study Period/Analysis	Patient Population	Baseline Observation	Post-baseline Observation(s)
		All Prior History: All CGAP Visits 1 – 3 including lifetime ^a	
C-SSRS categorical analyses for improvement	Safety population with a baseline and at least 1 post-baseline C-SSRS assessment	EM: Visit 3 CM: Last of CGAP Visit 1-3.	Last of 3.01–16
Treatment emergent abnormal laboratory values	Safety Population with normal laboratory values at all nonmissing baseline visits (with respect to direction being analyzed) and who have at least 1 post-baseline observation	EM: Visit 3 CM: All Visits 1–3	All Visits 3.01–16
Treatment emergent immunogenicity	Safety Population. ADA follow-up cohort (See Section 5.5.12.1.6)	EM (LY120/LY120, LY240/LY240): CGAN Visit 3 EM (PLA/LY120, PLA/LY240): CGAP Visit 3 CM: Visit 3	All Visits 3.01–16
Treatment emergent changes in vital signs, weight, and ECGs	Safety Population with a baseline and at least 1 post-baseline observation	EM: Visit 3 CM: Low: Minimum value from Visits 1–3 High: Maximum value from Visits 1–3	Low: Minimum value from Visits 3.01–16 High: Maximum value from Visits 3.01–16
Continuous safety analyses	Safety Population with a baseline and at least 1 post-baseline observation	EM: Visit 3 CM: Last of Visits 1–3	Scheduled visits: 3 < Visits ≤ 16
Study Period III and IV combined			
Efficacy analyses	ITT Population with a baseline and at least 1 post-baseline observation	Visit 3	All Visits 3.01-18
Quality of Life analyses	ITT Population with a baseline and at least 1 post-baseline observation	Visit 3	All Visits 3.01-18

Study Period/Analysis	Patient Population	Baseline Observation	Post-baseline Observation(s)
Continuous safety analyses	Safety Population with a baseline and at least 1 post-baseline observation	EM: Visit 3 CM: Last of Visit 1- 3	All Visits 3.01-18
Treatment emergent immunogenicity	ADA follow-up cohort (See Section 5.5.12.1.6)	EM (LY120/LY120, LY240/LY240): CGAN Visit 3 EM (PLA/LY120, PLA/LY240): CGAP Visit 3 CM: Visit 3	All Visits 3.01–18
Study Period IV			
Continuous safety analyses – change from baseline to LOCF endpoint (ANCOVA)	Post-treatment Population with a baseline and at least one post-baseline observation	EM: Last of Visits 3-16 CM: Last of Visits 1-16	Last Visit: 16.01-18
FEAEs	Post-treatment Population	EM: All Visits in CGAN Visit 1 - 16. CM: All Visits 1- 16. Pre-existing condition that is still ongoing at Visit 1 should be evaluated as baseline values.	All Visits 16.01–18
Serious Adverse Events, Discontinuations due to Adverse Events	Post-treatment Population	NA	All Visits 16.01–18
Follow-up emergent abnormal laboratory values	Post-treatment Population with normal laboratory values at all nonmissing baseline visits (with respect to direction being analyzed) and who have at least 1 post-baseline observation	EM: All Visits 3- 16 CM: All Visits 1- 16	All Visits 16.01–18
Follow-up emergent changes in vital signs, weight and ECGs	Post-treatment Population with a baseline and at least 1 post-baseline observation	EM: Low: Minimum value from Visits 3–16 High: Maximum value	Low: Minimum value from Visits 16.01–18 High: Maximum value from Visits 16.01–18

Study Period/Analysis	Patient Population	Baseline Observation	Post-baseline Observation(s)
		from Visits 3–16 CM: Low: Minimum value from Visits 1–16 High: Maximum value from Visits 1–16	
C-SSRS categorical analyses	Post-treatment Population with a baseline and at least 1 post-baseline C-SSRS assessment	EM: Recent History: CGAP Visit 3-16 All Prior History: All CGAN Visits 1-12 including lifetime ^a and All CGAP Visits 3.01-16 CM: Recent History: All CGAP Visits 1–16 excluding lifetime ^a All Prior History: All CGAP Visits 1-16 including lifetime ^a	All Visits 16.01–18
C-SSRS categorical analyses for improvement	Post-treatment Population with a baseline and at least 1 post-baseline C-SSRS assessment	EM: Last of CGAP Visits 3.01-16 CM: Last of CGAP Visits 3.01-16	Last of 16.01–18

Abbreviations: ADA = Anti-Drug Antibody; CM = chronic migraine; C-SSRS = Columbia Suicide Severity Rating Scale; EM = episodic migraine; FEAE = follow-up emergent adverse event; ITT = intent-to-treat; PPS = per protocol set; TEAE = treatment emergent adverse event.

Note: Visit 3.01 indicates the first unscheduled visit occurring after Visit 3 and prior to Visit 4. Other visits can be interpreted in a similar manner. For example, Visit 12.01 indicates the first unscheduled visit occurring after Visit 12 and prior to Visit 13. For efficacy and quality of life measures without unscheduled visits data point, Visit 3.01 indicates scheduled collection visits after visit 3.

^a Lifetime is captured in the C-SSRS visit 1 CRF (EM: CGAN visit 1, CM: CGAP visit 1).

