- Section 5.4.3.1: MSQ responder analysis was modified. For MSQ Role Function-Restrictive domain responder analysis, cutoff value was changed from 25 (for both EM and CM patients) to 17.14 for CM patients (the cutoff for EM patients remains the same as 25) to align global studies I5Q-MC-CGAG (CGAG) and I5Q-MC-CGAI (CGAI).
- Section 5.4.3.4: There was a typo. PSMQ-M was collected at Month 16 (SP IV). Hence, it was added. Descriptive summary for Month 16 was added ([Table CGAP. 5.5](#) and [Section 5.5.11.4](#))
- Section 5.5.1: For efficacy and QoL analysis, analysis arm was changed. Originally (SAP Ver.2) it was statistical models (MMRM, GLIMMIX, logistic regression) with 4 arms (EM120, EM240, CM120, CM240). The updated analysis (SAP Ver. 3) are,
 - [1] Statistical models with 2 arms (CM120, CM240)
 - [2] Descriptive summary for 6 arms (LY120/LY120, LY240/LY240, PLA/LY120, PLA/LY240, CM120, CM240)

The reason of this change is as follows; Based on the interim DBL and SAP Ver.2 analysis, we conducted preliminary analysis, i.e., the model based analysis (4 arms). Because the impact of the baseline difference (EM and CM patients) on post baseline estimation was not well captured as expected. In addition. All listings will be by 6 arms instead of 4 arms unless otherwise specified.

Note: Originally, descriptive summary for 6 arms was planned in SAP Version 1.

- Section 5.5.1: For safety analysis, treatment definition in statistical models are clarified as 4 arms (EM120, EM240, CM120, CM240).
- Section 5.5.1: For listing, 6 arms (LY120/LY120, LY240/LY240, PLA/LY120, PLA/LY240, CM120, CM240) will be used. Originally, it was planned with 4 arms (EM120, EM240, CM120, CM240).
- Section 5.5.1: For descriptive summary, standard error was added, in addition to standard deviation.
- Section 5.5.1.1: Treatment definition as covariate was clarified for efficacy, QoL, and safety.
- Section 5.5.1.1: Covariate for QoL analysis was clarified.
- Section 5.5.1.1: Log-rank test was updated. Stratification factor was deleted. Treatment comparison is CM120 vs CM240 only.
- Section 5.5.1.1: Kaplan-Meier plot was clarified based on 6 arms.
- Section 5.5.1.4, [Table CGAP. 5.4](#):
 - For TEAEs in SP III for EM patients, baseline was corrected from “CGAP Visit 3” to “CGAN Visit 1 to CGAP Visit 3”.

- For FEAEs in SP IV for EM patients, baseline was corrected from “CGAP Visit 3 to CGAP Visit 16” to “CGAN Visit 1 to CGAP Visit 16”.

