5.5.1. General Considerations

Unless otherwise specified, analyses will be conducted on an intent-to-treat (ITT) population, which will include all patients who are randomized at Visit 3 and receive at least 1 dose of study drug. Patients in the ITT population will be analyzed according to the treatment group to which they are randomized. When change from baseline is assessed, the patient will be included in the analysis only if he/she has a baseline and a post-baseline measurement.

Unless specified otherwise, data will be reported by the following treatment groups.

- EM120: EM patients who are randomized to galcanezumab 120 mg in Study CGAP
- EM240: EM patients who are randomized to galcanezumab 240 mg in Study CGAP
- CM120: CM patients who are randomized to galcanezumab 120 mg in Study CGAP
- CM240: CM patients who are randomized to galcanezumab 240 mg in Study CGAP

For some reports, following groups will be used:

- LY120/LY120: Study CGAN 120 mg galcanezumab with a loading dose/Study CGAP 120 mg galcanezumab with placebo injection for a loading dose
- LY240/LY240: Study CGAN 240 mg galcanezumab/Study CGAP 240 mg galcanezumab
- PLA/LY120: Study CGAN placebo/Study CGAP 120 mg galcanezumab with a loading dose
- PLA/LY240: Study CGAN placebo/Study CGAP 240 mg galcanezumab
- EM_ALL: all EM patients from Study CGAN (= EM120 + EM240)
- CM_ALL: all CM patients started from Study CGAP (= CM120 + CM240)
- LY_ALL: all patients (EM_ALL + CM_ALL)

Frequency tables such as AE or TEAEs will be sorted by total (LY_ALL) in decreasing frequency.

When 4 arms (EM120, EM240, CM120, CM240) are displayed and statistical comparisons are made, then it will be based on (EM120 vs EM240, CM120 vs CM240), unless otherwise specified.

When 3 arms (EM_ALL, CM_ALL, LY_ALL) are displayed and statistical comparisons are made, then it will be based on EM_ALL and CM_ALL, unless otherwise specified.

For efficacy and QoL analysis, descriptive statistics will be used. They will be displayed by 6 arms (LY120/LY120, LY240/LY240, PLA/LY120, PLA/LY240, CM120, CM240). There will be no statistical comparison among arms. In the summary of continuous variables, the mean, standard deviation, standard error, minimum, median, and maximum will be reported.

For efficacy and QoL analysis, in addition to the descriptive statistics, when statistical model is used such as MMRM, GLIMMIX, logistic regression, then 2 arms (CM120, CM240) will be used with statistical comparisons between arms.

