5.5.12.1.1. Adverse Events

Treatment-emergent adverse events are defined as the reported AEs that first occurred or worsened during the post-baseline phase compared with the baseline phase. Pre-existing condition that is still ongoing at Visit 1 for CM patients should be evaluated as baseline values. For each TEAE, the severity level of the event (mild, moderate, or severe) will be determined by patient or physician opinion. The MedDRA Lowest Level Term (LLT) will be used in the treatment emergent computation. For each LLT, the maximum severity at baseline will be used as the baseline severity. If the maximum severity during post-baseline is greater than the maximum baseline severity, the event is considered to be treatment-emergent for the specific post-baseline period. For each patient and TEAE, the maximum severity for the MedDRA level being displayed (PT, High Level Term, or SOC) is the maximum post-baseline severity observed from all associated LLTs mapping to that MedDRA level.

Follow-up emergent adverse events (post-treatment emergent adverse events) are defined similarly. They are events that first occurred or worsened during the follow-up period (Study Period IV) when compared to the baseline (SP I, SP II, and SP III). Pre-existing condition that is still ongoing at Visit 1 for CM patients should be evaluated as baseline values. (See detail definitions in [Table CGAP. 5.4](#))

For events that are gender-specific, the denominator and computation of the percentage will include only patients from the specific gender.

Following summary will be created:

- Overview of AE (SP III)
- TEAEs (SP III)
 - By PT by decreasing frequency
 - By SOC/PT
 - By maximum severity/PT
- FEAEs (SP IV)
 - By PT by decreasing frequency
 - By SOC/PT
 - By maximum severity/PT
- TEAEs by considered to be related to investigational product by investigator (SP III)
- Treatment Emergent Adverse Events that started on Treatment phase and Continuing in Post-Treatment Phase (SP III, SP IV combined)
- SAEs (SP III, SP IV separately)
- AEs leading to discontinuation (SP III, SP IV separately)

Following tables are created by 6 arms (with LY_ALL) without statistical tests:

- TEAEs (SP III) by SOC/PT
- TEAE by considered to be related to investigational product by investigator (SP III)

Listing of Subjects with TEAE or FEAE (SP III, SP IV combined) will be created.

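### The SP III TEAE reference period for LY/LY patients includes about 6 months on galcanezumab, and no all-onset table by 6 arms shows which recurring events this removes

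*SAP*

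**What the plan says.** SAP Table CGAP. 5.4 defines the Study Period III (SP III) TEAE baseline as "EM: CGAN Visit 1 – CGAP Visit 3 CM: All Visits 1–3". The Revision History shows that Version 3 chose this on purpose: "For TEAEs in SP III for EM patients, baseline was corrected from" CGAP Visit 3 alone to the longer window.

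SAP 5.5.12.1.1 works at the MedDRA lowest level term (LLT) and takes the maximum severity in the reference period as the baseline: "If the maximum severity during post-baseline is greater than the maximum baseline severity, the event is considered to be treatment-emergent".

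Two adverse event tables separate the EM treatment histories ("Following tables are created by 6 arms (with LY_ALL) without statistical tests"), and both are TEAE tables. The general listing is described as "Listing of Subjects with TEAE or FEAE (SP III, SP IV combined) will be created". All other adverse event tables use the default 4 arms (SAP 5.5.12), so EM120 and EM240 each pool LY/LY with PLA/LY. Where 4 arms are compared, "then it will be based on (EM120 vs EM240, CM120 vs CM240), unless otherwise specified"; SAP 5.5.12.1 specifies Fisher's exact test for SP III.

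In the same Table CGAP. 5.4 the immunogenicity baseline does depend on the CGAN arm: "EM (LY120/LY120, LY240/LY240): CGAN Visit 3 EM (PLA/LY120, PLA/LY240): CGAP Visit 3".

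**The concern.** The EM window is the same in calendar terms but not in exposure. LY/LY patients received in CGAN the dose that they continue in CGAP, PLA/LY patients received placebo, and the CM window ends at the first dose. For LY/LY patients the rule therefore asks whether an event is new or worse compared with a period already on drug. Recurring drug-related events, of which injection-site reactions are the obvious candidate, are the ones most likely to fail that test.

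TEAEs come first in the endpoint list for the primary objective, long-term safety over 1 year of treatment (Table CGAP. 4.1). A lower LY/LY rate in the 6-arm tables could reflect tolerance, selection of patients who completed CGAN treatment, or the counting rule, and the planned outputs do not let a reader tell these apart.

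**Working it through.** **The plan's own figure.** SAP 5.2 plans about 150 patients per arm with 30% non-completion, for at least 100 per arm at 1 year: 150 × 0.70 = 105. This is consistent, and the point does not depend on it.

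**Exposure inside the reference period**
- First CGAN injection: CGAN Visit 3 (SAP 5.5.8).
- End of CGAN treatment: CGAN Visit 12, which is CGAP Visit 3 (SAP 5.1.1).
- Length: about 6 months, inferred because SAP 5.5.4 uses CGAN Month 6 as the EM baseline month.
- Dose: unchanged for patients from the galcanezumab arms (SAP 5.3.1).

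**Where a recurrence of the same LLT at no greater severity is counted for an LY/LY patient**
- TEAE tables, including both 6-arm tables: no.
- Registry 'Other' set (SAP 5.9, limited to non-serious TEAEs): no.
- SAEs and discontinuations due to adverse events: yes if it qualifies, because Table CGAP. 5.4 applies no baseline to them.
- Potential-hypersensitivity summary, injection-site summary by anatomical location and the two duration figures (SAP 5.5.12.1.1.1 and 5.5.12.1.1.2): possibly, since they are not worded as TEAE-only. They cover only their own event classes.

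**Closed-form illustration.** Assume one LLT, a constant rate equal in all patients, 6 months of reference and 12 months of observation, and no credit for worsening. With true 12-month risk r, the LY/LY TEAE rate is r × (1 − r)^(6/12):
- r = 10%: 0.10 × 0.949 = 9.5%
- r = 30%: 0.30 × 0.837 = 25.1%
- r = 50%: 0.50 × 0.707 = 35.4%

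**Simulation, with worsening credited.** Further assumptions, none from the documents: severity mild/moderate/severe 70/25/5%; gamma between-patient variation with CV 0, 1 or 2; event rate on placebo 25% of the on-drug rate; no dropout.

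| True 12-month risk | LY/LY TEAE rate (CV 0 / 1 / 2) | PLA/LY TEAE rate (CV 0 / 1 / 2) | PLA/LY minus LY/LY, points |
|---|---|---|---|
| 10% | 9.6 / 9.2 / 8.4% | 9.9 / 9.8 / 9.5% | 0.3 / 0.6 / 1.1 |
| 20% | 18.4 / 17.2 / 14.8% | 19.6 / 19.2 / 18.3% | 1.2 / 2.0 / 3.5 |
| 30% | 26.4 / 23.9 / 20.1% | 29.1 / 28.2 / 26.6% | 2.7 / 4.3 / 6.5 |
| 50% | 39.3 / 34.5 / 27.6% | 47.0 / 45.0 / 41.5% | 7.7 / 10.5 / 13.9 |

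The last column is the part specific to active drug in the window. For an event equally frequent on placebo and on drug it would be zero.

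**Share of each EM arm.** Placebo patients split 1:1 (SAP 5.3.1) and 120 EM patients are planned per arm (SAP 5.2.1). CGAN allocation is not given. With a the fraction in each CGAN galcanezumab arm, q the placebo fraction and equal roll-over, the LY/LY share is a / (a + q/2):
- placebo:120:240 = 2:1:1: 0.25 / (0.25 + 0.25) = 50%, or 60 of 120
- 1:1:1: 0.333 / (0.333 + 0.167) = 67%, or 80 of 120

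At 30% true risk the drug-specific gap is then 0.027 × 60 = 1.6 to 0.065 × 80 = 5.2 patients per EM arm. At 10% it is 0.003 × 60 = 0.2 to 0.011 × 80 = 0.9.

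**The case against.** The definition is deliberate and openly stated, and new or worse since entering CGAN is a recognised meaning of treatment-emergent. Windows that include time on drug occur elsewhere in Table CGAP. 5.4: the reference period for follow-up-emergent events includes SP III. The immunogenicity contrast is loose, because that baseline is a titre at one visit and not a maximum over a period. All of this stands, and the point does not ask for a different main definition.

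A reader might infer more than the documents support:
- *That only LY/LY rates fall short of the all-onset rate.* No arm's TEAE rate is an all-onset rate. PLA/LY patients carry the CGAN window on placebo and CM patients carry Visits 1 to 3. Only the active drug in the window is specific to LY/LY.
- *That these events vanish from all reporting.* SAEs and discontinuations are unaffected, and some hypersensitivity and injection-site outputs may be unfiltered. The SAP does not say whether the TEAE/FEAE listing shows every event of a listed patient or only qualifying records.
- *That readers of the tables will not be told.* The SAP text requires no such note, but table shells, the main protocol and the CGAN documents are not among the documents.
- *That the EM120 against EM240 comparison is biased.* With equal event rates and equal LY/LY shares, the rule creates no false dose difference. It can narrow a real one for recurring events: in the simulation, 30% against 50% appears within LY/LY as 12.9, 10.6 or 7.5 points (CV 0, 1, 2) and not 20.

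The 6-arm TEAE tables are a real mitigation, since LY/LY can be read apart from PLA/LY. They still apply the TEAE filter, so they show a difference without explaining it.

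**Conclusion.** The point holds as a minor one. For LY120/LY120 and LY240/LY240, a recurring drug-related event that is neither more severe than in CGAN, nor serious, nor a cause of discontinuation is left out of the TEAE tables. No planned summary by 6 arms counts all onsets in the CGAP year. EM120, EM240 and LY_ALL mix this history with galcanezumab-free ones.

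The true size cannot be derived from the documents and may be zero. The figures above illustrate it under a constant on-drug rate, with no tolerance and no selection at roll-over. They indicate a negligible effect for rare events and a visible one for common, recurring events. The mechanism rests on the SAP text alone; only the 6-month length is inferred.

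**What to change.** Keep the current TEAE definition as the main one, and add:

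1. One descriptive supplementary table of all adverse events with onset in SP III, regardless of earlier occurrence or severity, by SOC and preferred term, for the 6 arms with LY_ALL and without tests. Include injection-site and hypersensitivity terms. Show events ongoing at CGAP Visit 3 that worsen in SP III in a separate row or with a flag, since they are not new onsets.
2. A matching listing.
3. A label on the EM TEAE tables stating that the reference period includes CGAN galcanezumab treatment for LY/LY patients. On its own this would not be enough, because it does not show the missing counts.

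The cost is one table, one listing and one label from data already collected. The downside is a second adverse event count that must be explained, with less favourable rates in that table. The contents of the adverse event overview, and whether the main duration figures are TEAE-only, are separate clarity questions.
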